### 9.1 Complete Remission (CR)

Complete remission is defined as the following:

- Bone marrow blasts <5%
- Absence of circulating blasts and blasts with Auer rods
- Absence of extramedullary disease
- ANC  $\geq$  1000/mm^3
- Platelet count  $\geq$  100,000/mm^3

### 9.2 Complete Remission with incomplete hematologic recovery (CRi)

Requires that all the same response criteria in peripheral blood and bone marrow as CR with the exception of the following:

- Residual neutropenia (<1000/mm^3) or
- Residual thrombocytopenia (<100,000/mm^3 independent of platelet transfusions)

### 9.3 Morphologic Leukemia-Free State (MLFS)

- Bone marrow blasts <5%
- Absence of blast with Auer rods
- Absence of extramedullary disease
- No hematologic recovery required

Marrow should not merely be “aplastic”. At least 200 cells should be enumerated or cellularity should be at least 10%.

### 9.4 Partial Remission (PR)

- All hematologic criteria of CR
- Decrease of bone marrow blast percentage to 5% to 25%

- Decrease of pretreatment bone marrow blast percentage by at least 50%

9.5 Stable Disease

Absence of CR, CRi, PR, MLFS; and criteria for PD not met.

Period of stable disease should last at least 3 months.

9.6 Treatment Failure

Primary Refractory Disease: No CR or CRi after 2 courses of intensive induction treatment or recovery with blasts/loss of CR/CRi within 28 days of documentation of initial CR/CRi. Exclude patients with death in aplasia or death due to indeterminate cause.

Death in Aplasia: Deaths occurring  $\geq 7$  days following completion of initial treatment while cytopenic; with an aplastic or hypoplastic bone marrow obtained within 7 days of death, without evidence of persistent leukemia.

Death from Indeterminate Cause: Deaths occurring before completion of therapy, or  $<7$  days following its completion; or deaths occurring  $\geq 7$  days following completion of initial therapy with no blasts in the blood, but no bone marrow examination available.

9.7 Progressive Disease (PD)

Evidence for an increase in bone marrow blast percentage and/or increase of absolute blast counts in the blood:

- $>50\%$  increase in marrow blasts over baseline (a minimum 15% point increase is required in cases with  $<30\%$  blasts at baseline; or persistent marrow blast percentage of  $>70\%$  over at least 3 months; without at least a 100% improvement in ANC to  $500/\text{mm}^3$  and/or platelet count to  $>50,000/\text{mm}^3$  non-transfused); or
- $>50\%$  increase in peripheral blasts (White Blood Count (WBC)  $\times$  % blasts) to  $>25,000/\text{mm}^3$  (in the absence of differentiation syndrome); or
- New extramedullary disease

“Progressive disease” is usually accompanied by a decline in ANC and platelets and increased transfusion requirement and decline in performance status or increase in symptoms.

9.8 Relapse

Relapse following CR/CRi is defined as (only if this happens  $>28$  days after CR/CRi):

Bone marrow blasts  $\geq 5\%$ ; or reappearance of blasts in the blood; or development of extramedullary disease.

## 10. Study Parameters

- Pre-study assessments should be done  $\leq$  48 hours prior to randomization (except for bone marrow biopsy, thyroid function testing, pregnancy testing, ECG and left ventricular ejection fraction which can be done  $\leq$  2 weeks).

Procedures	Pre-screen	Screening/ Prior to Randomization	Induction*					Consolidation*			End of Treatment 	Follow- Up 
			Daily	Weekly	Day 21 from Start of Cycle 1 Induction	Prior to 2 nd Induction, if applicable	End of Induction	Prior to Each Consolidation Cycle	Weekly	End of Consolidation Cycle 1		
Written Informed Consent	X 	X										
Disease Characteristics 		X										
Medical/Surgical History		X										
Assessment of Baseline Signs & Symptoms		X										
Height		X										
Physical Exam		X	X 			X		X	X 		X	
Vital Signs (Temperature, Pulse, Blood Pressure)		X	X 			X		X			X	
Weight 		X				X		X			X	
BSA		X				X		X				
Performance Status		X		X		X		X			X	
CBC/Differential/ Platelets 		X	X 			X		X	X 		X	
Chemistry 		X		X 		X		X	X 		X	
Liver Functions 		X		X 		X		X	X 		X	
Thyroid Function Tests (T4 & TSH) 		X									X	
Serum Pregnancy Test 		X										
Left Ventricular Ejection Fraction (MUGA or ECHO) 		X				X 						

Procedures	Pre-screen	Screening/ Prior to Randomization	Induction*					Consolidation*			End of Treatment 	Follow- Up 
			Daily	Weekly	Day 21 from Start of Cycle 1 Induction	Prior to 2 nd Induction, if applicable	End of Induction	Prior to Each Consolidation Cycle	Weekly	End of Consolidation Cycle 1		
12-Lead ECG (QTcF Interval) 		X 		X 	X 	X 			X 		X 	
Local Bone Marrow Aspirate/Biopsy (Mandatory)	X 				X 		X 			X	X  Optional	X 
Research Bone Marrow Samples Submission (Mandatory) 	X 						X			X		X 
Protocol Therapy Administration 			X					X				
Concomitant Medications 		X	X 			X		X			X	
Adverse Events Assessment			X 			X		X			X 	
Survival Status												X

\* **Scheduled Visits:** Delay due to holidays, weekends, bad weather or other unforeseen circumstances will be permitted.

\*\* If prophylactic lumbar puncture is performed, recommend scheduling so results are available prior to Day 8 or wait until Day 21 to perform.

1 Any patient undergoing bone marrow biopsy with suspicion of or known diagnosis of AML will be asked to sign a Prescreening Consent in order to obtain baseline immunophenotyping and determination/confirmation of FLT3 status and obtain research samples for the study prior to randomization. FLT3 (includes signal ratio), NPM1 and DNMT3 mutation status will be performed on all patients. These tests will be completed at Central Labs. See Section 13.1, Invivoscribe Lab Manual and PrE0905 Lab Manual for details. **FLT3 and NPM1 mutation status results must be available on all patients.** Patients must have known FLT3 mutation and will be stratified according to TKD vs. ITD FLT3 mutation. Patients with FLT3-ITD mutation will undergo further stratification with NPM1 mutation status (positive vs. negative) and signal ratio (high [ $\geq 0.5$ ] vs. low [ $<0.5$ ] of FLT3 Wild Type).

For patients who are registered with tissue submitted for the study and are FLT3 negative or other condition, no further information will be collected after baseline demographics, sample submission, sample results and final diagnosis.

2. Record date of diagnosis (date of diagnostic bone marrow biopsy), primary tumor type, histology, cytogenetics and molecular markers.

3 **Induction:** Daily if admitted to hospital, otherwise weekly until count recovery.

**Consolidation:** May be done locally after Day 8 visit per institutional guidelines.

4. Per Study Parameters and as clinically indicated.

5 CBC with differential and platelet count which includes WBC, ANC, Platelets, Hemoglobin, and Hematocrit. Additionally, required within 24 hours prior to each cycle of chemotherapy.

- 
- 6 **Induction:** Differential daily until disappearance of peripheral blasts, then twice weekly at nadir, after peripheral blasts gone and while WBC <500. If the patient is discharged prior to recovery of WBC ( $\geq 500$ ), obtain differential twice weekly until end of induction, then per institutional guidelines until consolidation starts.  
**Consolidation:** Twice weekly or per institutional guidelines.
- 7 BUN/creatinine, uric acid, sodium, potassium, chloride, glucose, calcium, magnesium, and phosphorus. Additionally, required within 24 hours prior to each cycle of chemotherapy.
- 8 **Induction:** Twice weekly.  
**Consolidation:** Weekly or per institutional guidelines.
- 9 AST, ALT, and total bilirubin. If total bilirubin  $\geq 2$ , obtain direct bilirubin (if direct bilirubin  $\geq 2$ , refer to Section 6.1 for Dose Modifications/Interruptions). Additionally, required within 24 hours prior to each cycle of chemotherapy.
- 10 Thyroid Function test results not required for randomization.
- 11 Required for sexually active females of child-bearing potential.
- 12 LVEF must be obtained before initiating second induction cycle (if applicable) and must use same method as initial assessment.
- 13 Perform 12-lead ECG in triplicate (3 separate ECGs recorded at least 5 minutes apart) following a 10 minute resting period. Patient may not have QTcF interval >500 msec or Long QT Syndrome.  
**Calculation of QTc interval using the Fridericia formula:**  
[https://qxmd.com/calculate/calculator\\_48/ecg-corrected-qt](https://qxmd.com/calculate/calculator_48/ecg-corrected-qt)
- 14 Perform 12-lead ECG in triplicate (3 separate ECGs recorded at least 5 minutes apart) following a 10 minute resting period prior to gilteritinib or midostaurin administration (ECG within 1 hour of dosing preferred). The mean QTcF of the triplicate ECG tracings will be used for final treatment decisions and AE reporting. If the mean of the triplicate QTcF is >500 msec, then triplicate ECGs will be repeated (within 2 hours). If the repeat ECGs confirm a mean QTcF >500 msec, refer to Section 6.1.2 and Section 6.1.3 for further guidance on treatment decision. In addition, on Cycle 1, Day 15 if QTcF is increased >30 msec over screening, repeat ECG on Day 16 and refer to Section 6.1.2 for further guidance on treatment decision.
- Induction (First Induction)**  
Day 8, Day 15 and Day 21
- Second Induction and Consolidation**  
Day 8 of each cycle
- See footnote 13 for Calculation of QTc interval using the Fridericia formula.**
- 15 Perform 12-lead ECG in triplicate (3 separate ECGs recorded at least 5 minutes apart) following a 10 minute resting period.  
**See footnote 13 for Calculation of QTc interval using the Fridericia formula.**
- 16 +/- 1 day window (Delays due to holidays, weekends, or other unforeseen circumstances will be permitted).
- 17 For patients that receive 1 cycle of induction, no later than Day 60 after initiation of first cycle of induction therapy. For patients that receive 2 cycles of induction, no later than Day 60 after initiation of the second cycle of induction therapy (i.e., Day 84-105). [MRD sample will be obtained by Day 60 on all patients even if counts have not recovered. The only exception is a patient who has been declared a relapse based on blood counts.]
-

- 18 Optional, after last cycle of consolidation per institutional guidelines.
- 19 Optional, at time of relapse, bone marrow samples are requested to be sent for correlative studies (Section 13.1).
- 20 **Mandatory Research Bone Marrow Samples:** See Section 13.1, Invivoscribe Lab Manual and PrE0905 Lab Manual for details.

**Prescreening**

Invivoscribe: One 4 mL sodium heparin green top tube

- If bone marrow sample (preferred) is not available, then one 4 mL Sodium Heparin green top tube of peripheral blood will be allowed if patient has any circulating blasts.

CBPF: Two 10 mL EDTA tubes

- If diagnostic bone marrow was done prior to study enrollment or patient is inaspirable, then two 10 mL EDTA tubes of peripheral blood will be allowed if patient has any circulating blasts.

**End of Induction (First and Second Induction, as applicable)**

Invivoscribe: If FLT3 ITD+, one 4 mL EDTA tube (bone marrow)

CBPF: All patients (ITD+ and/or TKD+), one 10 mL EDTA tube (bone marrow)  
If FLT3 TKD+, one additional 10 mL EDTA tube (bone marrow)

**NOTE:** Patients are not eligible to proceed to consolidation unless bone marrow samples are obtained for MRD at time of CR/CRI.

**End of First Cycle of Consolidation**

Invivoscribe: If FLT3 ITD+, one 4 mL EDTA tube (bone marrow)

CBPF: All patients (ITD+ and/or TKD+), one 10 mL EDTA tube (bone marrow)  
If FLT3 TKD+, one additional 10 mL EDTA tube (bone marrow)

**Relapse (OPTIONAL)**

CBPF: Two 10 mL EDTA tubes (bone marrow)

**Optional:** Any leftover tissue banked for future research.

21 **INDUCTION:**

Standard of care induction 7+3 chemotherapy may start prior to randomization using same regimen and dose as defined in Section 5.2.1 while awaiting prescreening test results.

**Arm A (7+3 + Gilteritinib)**

- **Cytarabine** 100 mg/m^2/day will be administered by continuous IV infusion for a total of 7 days beginning Day 1
- **Daunorubicin** 90 mg/m^2/day will be administered IV per package insert or institutional guidelines or over 30-60 minutes Days 1,2,3 (45 mg/m^2/day if receives second cycle of induction)
- **Gilteritinib** 120 mg orally QD x 14 days starting on day 8

If second cycle of induction is needed, treatment will begin after Day 28 (i.e.,  $\geq 7$  days after completing gilteritinib) but no later than Day 45.

**ARM B (7+3) + Midostaurin**

- **Cytarabine** 100 mg/m^2/day will be administered by continuous IV infusion for a total of 7 days beginning Day 1
- **Daunorubicin** 90 mg/m^2/day will be administered IV per package insert or institutional guidelines or over 30-60 minutes Days 1,2,3 (45 mg/m^2/day if receives second cycle of induction)
- **Midostaurin** 50 mg orally BID x 14 days beginning on day 8

If second cycle of induction is needed, treatment will begin after Day 24 (i.e.,  $\geq 3$  days after completing midostaurin) but no later than Day 45.

If there is a delay in starting FLT3 inhibitors in Arm A or Arm B (due to obtaining drug, i.e. insurance, formulary, etc.), the FLT3 inhibitor will need to stop after Day 21 dose (i.e., Day 21 or Day 22 [if FLT3 inhibitor started on Day 9]). No missed doses will be made up.

Prophylaxis with intrathecal chemotherapy is allowed prior to or during induction.

See Section 5 for dosing instructions and additional information for gilteritinib and midostaurin administration and Section 6 for dose delays/modifications. If CR or CRi is not achieved, a second induction cycle of therapy may be administered.

**NOTE:** Patients are not eligible to proceed to consolidation unless bone marrow samples are obtained for MRD at time of CR/CRi.

**CONSOLIDATION:**

**ARM A**

- **Cytarabine** 3 g/m^2\* over approximately 1-3 hours every 12 hours (+/- 2 hour window) on days 1,3,5 or days 1-3 for a total of 6 doses for up to 4 cycles
- **Gilteritinib** 120 mg orally QD x 14 days beginning on day 8 of each cycle (up to 4 cycles)

**ARM B**

- **Cytarabine** 3 g/m^2\* over approximately 1-3 hours every 12 hours (+/- 2 hour window) on days 1,3,5 or days 1-3 for a total of 6 doses for up to 4 cycles
- **Midostaurin** 50 mg orally BID x 14 days beginning on day 8 of each cycle (up to 4 cycles)

\* For patients age  $\geq 55$  or patients with decreased creatinine clearance recommend reducing consolidation cytarabine dose to 1.5 g/m^2.

If there is a delay in starting FLT3 inhibitors in Arm A or Arm B (due to obtaining drug, i.e. insurance, formulary, etc.), the FLT3 inhibitor will need to stop after Day 21 dose. No missed doses will be made up.

Prophylaxis with intrathecal chemotherapy is allowed prior to or during consolidation.

See Section 5 for dosing instructions and additional information for gilteritinib and midostaurin administration and Section 6 for dose delays/modifications.

**NOTE:** Patients deemed suitable by the treating investigator may proceed to allogeneic TRANSPLANT after induction or after 0-4 cycles of consolidation. Patients will go off treatment at the time of transplant or any non-protocol leukemia directed therapy after completion of the end of treatment visit.

22 Please review all concomitant medications. Section 6.2.2 for medications not permitted and Section 6.2.3 for medications to use with caution. Only record concomitant medications for SAE and/or AESI in eCRF.

23 Patients will be followed for adverse events for 30 days after their last dose of study medication. However, an adverse event occurring at any time after discontinuation of study therapy that is felt to be at least possibly related to study therapy should be recorded.

**NOTE:** Pregnancy within 180 days for WOCBP and for 120 days for a female partner of child-bearing potential after the final study drug administration will be reported and followed per Section 8.6.

- 24 Upon count recovery after last cycle of chemotherapy and completion of gilteritinib or midostaurin.
- 25 Every 3 months from end of treatment for 2 years, then every 4 months for 1 year, then every 6 months for 1 year, then annually for progression and survival until death or study closure (+/- 1 month) whichever comes first. Patients should be seen up to the 2 year point at the treating institution. If the patient is unable to be seen at the treating institution, copies of office visit notes including labs with local oncologist should be obtained until year 5 per schedule above. Initiation of all anticancer therapy for current remission and first anticancer therapy for relapse will be documented. If patient is removed from treatment for reason(s) other than progression or full consent withdrawal, follow for relapse/survival until death or study closure.

**NOTE:** For patients who are registered with tissue submitted for the study and are FLT3 negative, no further information or other condition will be collected after baseline demographics, sample submission, sample results and final diagnosis. For eligible patients randomized to the trial, but do not receive any protocol therapy, baseline, safety [as applicable] and end of treatment follow-up information will also be collected.

---

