#### 1.3.1 Clinical Pharmacokinetics (PK) and Pharmacodynamics

Single and multiple dose gilteritinib PKs were characterized in subjects with relapse or refractory AML enrolled in Study 2215-CL-0101. Results indicated gilteritinib exhibits linear, dose-proportional PKs from 20 mg to 450 mg. Assessment of  $C_{trough}$  at various time points indicated steady state is achieved by day 15 after multiple dose administrations of gilteritinib from 20 to 450 mg once daily. An ex vivo Plasma Inhibitory Activity (PIA) assay was used to assess target inhibition in subjects treated with gilteritinib. Samples collected pre-dose and post-dose on days 1, 8, 15 and 29 demonstrated marked and sustained inhibition of phospho-FLT3 at doses 80 mg and higher.

The effect of strong and moderate cytochrome P450 (CYP)3A inhibitors on gilteritinib exposure was assessed in relapsed or refractory AML subjects (Study 2215-CL-0101) and healthy subjects (Study 2215-CL-0108). In relapsed or refractory AML subjects, there was a less than 2-fold increase in gilteritinib exposure when gilteritinib was co-administered with moderate or strong CYP3A4 inhibitors. In healthy subjects, gilteritinib exposure increased approximately 2.2-fold when gilteritinib was co-administered with itraconazole, a strong CYP3A4

---

and P-glycoprotein (P-gp) inhibitor. The effect of rifampin, a strong CYP3A and P-gp inducer, on gilteritinib PKs was evaluated in healthy adult subjects (Study 2215-CL-0108). Co-administration of gilteritinib with rifampin, resulted in an approximate 70% decrease in gilteritinib exposure. Collectively, these data support monitoring subjects who require concomitant medications that are strong CYP3A4 inhibitors and restricting use of concomitant medications that are strong CYP3A4 inducers.

A subset of relapsed or refractory AML subjects (2215-CL-0101) were co-administered gilteritinib and cephalexin a MATE 1 substrate to evaluate a potential drug-drug interaction. Cephalexin exposure and urinary excretion were comparable after single dose administration of cephalexin alone and in combination with gilteritinib (administered once daily). These results suggest co-administration of MATE1 substrates and gilteritinib is not expected to result in a clinically-relevant drug-drug interaction.

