11.2.5 Drug Interactions

Midostaurin is metabolized by CYP3A4 to active compounds. Co-administration of drugs which are potent inducers (e.g., phenytoin) or, especially, potent inhibitors (e.g., itraconazole) of this isoenzyme could decrease or increase midostaurin concentrations, and, potentially, decrease the effectiveness or increase toxicity, respectively.

Potent CYP3A4 inhibitors are thought to represent the most significant potential for drug interactions with midostaurin (Appendix V).

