## 6.2. Concomitant Medications and Procedures

Concomitant medications and procedures will be collected during the trial and recorded in the CRF page.

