### **7.4.1. Safety Population**

Safety population is used for safety analysis. The safety population is defined as all patients treated with at least one dose of study medication during the study. All safety data collected up to the end of the study are included in the safety analysis.

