### **7.5.4. Concomitant Medications and Procedure**

The use of concomitant medications and procedure will be recorded on the CRFs. The concomitant medications will be coded to a World Health Organization Drug Dictionary (WHO-DD) term (Version WHODRUG Version - March 2016).

The use of concomitant medications and procedures will be summarized by arm and overall, for the safety population for induction and consolidation separately. In each of these summary tables, the number and percentage of patients taking each medication will be presented by ATC Classification.

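### The eCRF takes concomitant medications only for SAEs and AESIs, but the SAP tabulates them as use across all treated patients, so the table is incomplete and mislabelled

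*Protocol*

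**What the plan says.** Protocol Section 10, footnote 22 is attached to the concomitant medication row of the study calendar. It gives two instructions. Sites are told: "Please review all concomitant medications". The data entry rule is narrower: "Only record concomitant medications for SAE and/or AESI in eCRF". AESI is expanded in the protocol's abbreviation list, but neither document says which events it covers.

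SAP 6.2 describes collection with no such limit: "Concomitant medications and procedures will be collected during the trial and recorded in the CRF page". SAP 7.5.4 then plans a table in which "the number and percentage of patients taking each medication will be presented by ATC Classification". It is to be "summarized by arm and overall, for the safety population for induction and consolidation separately". The denominator is set by SAP 7.4.1: "The safety population is defined as all patients treated with at least one dose of study medication during the study".

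The SAP's copy of the calendar (Appendix I) carries no equivalent of footnote 22 on the concomitant medication row; note 22 in that appendix concerns the timing of the end-of-treatment visit. SAP Section 8 states that no changes from the protocol's analyses are planned.

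**The concern.** The numerator and denominator of the planned percentage come from different rules. To be counted, a patient must have taken the drug and must also have had it entered because of an SAE or AESI. To be in the denominator, a patient need only have had one dose of study medication. A treated patient who took the drug but had no qualifying event appears as a non-user.

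Two things follow. Percentages are too low in both arms. If SAEs or AESIs are recorded at different rates in the two arms, the arms can also appear to differ in drug use when they do not. Concomitant medication is one of the safety evaluations named in SAP Sections 6 and 7.5, so a study report reader would take the table at face value. The protocol gives such a reader a reason to look. Section 6.2.3 permits strong CYP3A inhibitors as standard anti-infectives, and Section 11.2.5 says of the control drug: "Potent CYP3A4 inhibitors are thought to represent the most significant potential for drug interactions with midostaurin".

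**Working it through.** The plan gives no figure for concomitant medication use, so there is nothing to reproduce. The check is a reconciliation of text, followed by arithmetic on assumed values to show direction and range.

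**Step 1. The rules side by side.**

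- Reviewed by the site: all concomitant medications (Protocol Section 10, footnote 22).
- Entered in the eCRF: only those for an SAE and/or AESI (same footnote).
- Assumed by the SAP to be entered: concomitant medications generally (SAP 6.2; Appendix I has no limit).
- Tabulated: patients taking each medication, by arm and phase (SAP 7.5.4).
- Denominator: everyone given at least one dose (SAP 7.4.1).
- Departure declared: none (SAP Section 8).

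**Step 2. What the table would show.** Let *u* be the true proportion of treated patients taking a drug and *c* the proportion of those users whose use is entered because of an SAE/AESI. Then:

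- displayed proportion = *u* × *c*
- undercount = *u* × (1 − *c*)
- apparent arm difference when true use is equal = *u* × (*c*A − *c*B)

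**Step 3. Assumed ranges.** The documents give neither *u* nor *c*. Take *u* from 50% to 90% and *c* from 30% to 70%:

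- lowest displayed value: 0.50 × 0.30 = 15%
- highest displayed value: 0.90 × 0.70 = 63%
- smallest undercount: 0.50 × (1 − 0.70) = 15 points
- largest undercount: 0.90 × (1 − 0.30) = 63 points

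Now take true use of 70% in both arms:

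- capture 50% v 50%: 35% v 35%, no false contrast, 35 points undercounted in each arm
- capture 60% v 40%: 42% v 28%, a false difference of 14 points
- capture 70% v 40%: 49% v 28%, a false difference of 21 points

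**Step 4. How *c* relates to event frequency.** This depends on what a medication for an SAE or AESI means. If it means everything taken around the time of the event, *c* is roughly the share of users with such an event, and the contrast follows event frequency. If it means drugs given to treat the event, prophylactic drugs may hardly be entered in either arm. The contrast for those drugs then shrinks towards zero and the undercount approaches the whole of true use. The undercount is present under both readings; the size of the contrast is not fixed by the documents.

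**The case against.** The strongest reply is that this is a wording mismatch in one descriptive table. No hypothesis is tested on it, and no efficacy analysis or adverse event table draws on it. The table templates and eCRF instructions are separate documents, and SAP 2.1 provides for a running note to the SAP, so the matter may already be settled elsewhere. Because the SAP's calendar lacks the limit, earlier patients may have been recorded under a wider rule. All of this limits the consequence. It does not remove the conflict between the two documents, and SAP Section 8 says there is nothing to declare.

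Several stronger readings are tempting and are not supported:

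- *The arm with more SAEs will seem to use more of every drug.* Step 4 shows that this depends on how the footnote is read.
- *Use is captured only in patients with serious events.* The footnote includes AESIs, and nothing says an AESI must be serious.
- *Inhibitors about double gilteritinib exposure.* Protocol 1.3.1 does report that "gilteritinib exposure increased approximately 2.2-fold when gilteritinib was co-administered with itraconazole", but in healthy subjects. In relapsed or refractory AML patients it reports a rise of less than 2-fold with moderate or strong inhibitors.
- *The raised exposure can be turned into an equivalent dose and set against the toxicities seen at 200 mg/day with chemotherapy.* The AML figure is an upper bound, and the documents do not say which inhibitors those patients were taking.
- *Inhibitor use is the one factor that alters effective dose.* Dose reductions, interruptions, late starts without make-up doses, and inducers alter it too.
- *The trial cannot separate gilteritinib toxicity from inhibitor-raised exposure, so adverse events should be compared with and without an inhibitor.* No objective or SAP section plans this. The groups would form after randomization, and anti-infectives are given for infection risk, so the comparison would be confounded by indication even with full recording.

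**Conclusion.** The plan is wrong as written on this point. The direction of the undercount follows from the text alone: unless every user's drug happens to be entered, the displayed percentages fall below true use in both arms. A false arm contrast arises only if capture differs between arms, and the documents do not show that it will. The size of either effect is unknown; the percentages in Step 3 are illustrations resting on assumed use and capture rates.

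The table is better called incomplete and mislabelled than useless. Under a title and denominator that match what was collected, it would be valid. The limit on comparing drug use applies to eCRF data; site records may hold more. The conclusion assumes that footnote 22 governs data entry and that the unseen templates and eCRF instructions do not already correct the SAP.

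**What to change.** Required:

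1. Rewrite SAP 6.2 to state the recording rule in footnote 22, and say whether it covers drugs given to treat the event, all drugs taken at the time, or both.
2. In SAP 7.5.4, retitle the medication table *medications recorded for SAE/AESI*. Use as denominator the patients with a recorded SAE or AESI in that phase, by arm and overall. Add a note that the table does not estimate use in all treated patients and that the arms are not compared as randomized.
3. List the AESI terms.
4. Declare the change in SAP Section 8. If earlier patients were recorded under a wider rule, say so and restrict the table to entries linked to an SAE or AESI.

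This costs SAP text, one revised table shell and an agreed AESI list. It needs no new patient data.

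Optional: for patients still on treatment, record strong CYP3A/P-gp inhibitor and inducer use (yes/no, with dates) for everyone in both arms, and tabulate it descriptively by arm. The exposure findings in Protocol 1.3.1 and the midostaurin statement in 11.2.5 are reason enough. The cost is modest site data entry, since sites already review these drugs. The benefit is limited by timing: Protocol 12.3.1 reports the response-rate interim analysis as complete, and the SAP is dated November 2023, so few patients may remain on treatment.
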